**NCT NUMBER: NCT03296553**

**DATE : JULY 23, 2015.**

## **STUDY PROTOCOL**

### **Objective:**

To evaluate the occurrence of severe immune reconstitution inflammatory syndrome associated to Kaposi Sarcoma (S-IRIS –KS) and its attributable mortality in patients with AIDS and disseminated KS (dKS) (pulmonary and/or skin disseminated, and/or lymphadenopathic, and/or generalized lymphedema, and/or gastrointestinal tract involvement) with the use of valganciclovir (ganciclovir prodrug, oral formulation) prior to the initiation of combined antiretroviral therapy (cART) compared with the standard management of immediate cART initiation.

### **Hypothesis:**

In patients with AIDS and disseminated KS administration of valganciclovir as an anti-HHV-8 agent can diminish viral replication prior to administration of cART, and thus decrease the frequency of S-IRIS-KS with a subsequent reduction on S-IRIS-KS attributable mortality.

### **Methodology:**

Open randomized clinical assay. Will include patients with AIDS and disseminated KS who accept to participate and sign informed consent.

### **Inclusion criteria:**

Patients >18 years old, HIV+ naïve to cART with dKS, able and willing to provide written informed consent.

DKS was defined as the presence of KS pulmonary disease and/or  $\geq 30$  KS skin lesions, with or without lymphedema, and/or lymph node involvement, and/or gastrointestinal tract KS involvement (biopsy-proven at least in one site).

### **Exclusion criteria:**

Another concomitant malignancy, Multicentric Castleman Disease (MCD), steroid treatment two months prior to screening, active Hepatitis B, Hepatitis C or CMV end-organ disease infection, and/or severely ill patients with APACHE II score >15 points.

The study will comprise two study groups:

1. Group 1: Patients will receive treatment with valganciclovir during 4 weeks prior to initiation of cART and/or continue for 48 weeks
2. Group 2: Patients will initiate standard treatment with cART.

Both groups receive chemotherapy with bleomycin/vincristine; according to treating physician.

### **Randomization**

Patients will be randomized by blocks of ten; the assigned group written in closed envelopes:

Experimental Group 1 (EG) will receive valganciclovir 900 mg twice daily for 48 weeks and initiate cART at week 4 after randomization.

Control Group 2 (CG) will start cART immediately according to current Mexican Guidelines.

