**Sample Size**

Sample size was calculated for a study power of 80% and an alpha of 0.05. Event rate in the control group was estimated as 40%, while that in the treated group was considered 5%. The number of resulting patients in each group is 19 for a total sample of 38 patients. This assumes a significant impact of treatment on S-IRIS-KS occurrence and its mortality.

The antiretroviral scheme will be assigned according to the criteria of the “The Antiretroviral Management Guide of Persons with HIV” in effect in Mexico.

Candidates will have an initial thorough clinical evaluation including a work-up to diagnose coinfections and rule out other neoplasms that comprise: ophthalmologic evaluation, computed tomography (CT) scan (neck, thorax, and abdomen), bone marrow culture with bone biopsy, Hepatitis B Virus (HBV) and Hepatitis C Virus (HCV) serology, venereal disease research laboratory (VDRL) test and if indicated lumbar puncture to rule-out neurosyphilis, Histoplasma urinary antigen and serology, and GenXpert MTB/RIF test. Upper gastrointestinal tract (GIT) endoscopy with biopsy of lesions; colonoscopy will be performed only on patients with diarrhea or lower-GIT bleeding. Biopsies of enlarged lymph nodes will be obtained and processed for histopathological analysis and culture. If indicated, bronchoscopy with bronchoalveolar lavage (BAL) will be performed as well as a thoracic Gallium 67 Spect-CT Scan or PET-FDG scans.

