### **Secondary outcomes:**

Total number of SIRS events (S-IRIS-KS and Non-S-IRIS-KS) in treated and control group. This is going to be done by a Poisson's models analysis adjusted by age, gender, coinfections, baseline: CD4, and viral load of HV8, C reactive protein, HIV VL, IL6, IL10, TNF, and IFN. We will compare mortality in patients with pulmonary KS between groups.

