**TITLE: Valganciclovir Four Weeks Prior to cART
Initiation Compared to Standard Therapy for
Disseminated Kaposi Sarcoma**

NCT number: 03296553

DATE: November 30, 2019.

Statistical analysis

Sample size was calculated for a study power of 80% and an alpha of 0.05, with an estimated event rate (IRIS) in the control group of 40%, and in the treated group of 5%. The number estimated in each group was 19, for a total sample of 38 patients.

Descriptive statistics were performed, including the number of deaths, and episodes of S-IRIS-KS, in the CG and EG groups. Comparisons between EG and CG were performed, as intention-to-treat (ITT), and as per-protocol analysis, for the primary outcome of mortality attributed to S-IRIS-KS using Proportional-Hazard Cox models.

In addition, we compared the impact of treatment on repeated episodes of S-IRIS-KS by multivariate Poisson model and by the number of participants with at least one S-IRIS-KS event, as repeated events can occur in the same patient, and the total number of events may be due to a few very susceptible individuals.

Statistical models were adjusted by baseline CD4+, CD4+/CD8+ cell ratio, HHV-8 and HIV VL, plasmatic IL-6, CRP and by the presence of concomitant coinfections. Analyses were performed using Stata Statistical program.

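### Pulmonary KS gets its own mortality comparison, yet neither the randomisation nor the listed mortality models account for it, so chance imbalance could tip or mask a borderline result in 38 patients

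*Protocol*

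**What the plan says.** - **Eligibility** (Protocol, Inclusion criteria): "DKS was defined as the presence of KS pulmonary disease and/or" at least 30 skin lesions, node disease or gastrointestinal disease. Lung disease is one of several alternative routes, so patients with and without it are enrolled together.
- **Allocation** (Protocol, Randomization): "Patients will be randomized by blocks of ten; the assigned group written in closed envelopes". No stratification factor is named.
- **Pulmonary KS and death** (Protocol, Secondary outcomes): "We will compare mortality in patients with pulmonary KS between groups". No other disease site has its own mortality comparison. The SAP does not mention pulmonary KS.
- **Mortality model, protocol** (Primary outcome): Cox regression, and also logistic regression, for all-cause mortality at 48 weeks. The minimum adjustment set is age, gender, CD4 and HHV-8 viral load.
- **Mortality model, SAP**: Cox models for mortality attributed to severe KS-IRIS. "Statistical models were adjusted by baseline CD4+, CD4+/CD8+ cell ratio, HHV-8 and HIV VL, plasmatic IL-6, CRP", and also by coinfections.
- **Baseline work-up** (Protocol, under Sample Size): candidates have a CT scan that includes the thorax, and bronchoscopy if indicated. Lung status can therefore be recorded before allocation.

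**The concern.** By giving pulmonary KS its own mortality comparison, the protocol signals that lung involvement matters for death. The plan then neither balances the arms on it nor names it in a model, although it adjusts for a series of laboratory values. With 19 patients per arm, a handful of extra pulmonary cases on one side is quite possible. If those patients die more often, the overall mortality contrast moves for a reason unrelated to valganciclovir, in either direction, and no listed adjustment is aimed at it.

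**Working it through.** **The plan's own figure.** "Sample size was calculated for a study power of 80% and an alpha of 0.05", with rates of 40% and 5%, and "The number of resulting patients in each group is 19 for a total sample of 38 patients". The two-sided normal approximation with unpooled variance gives

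n = (1.960 + 0.842)² × (0.40×0.60 + 0.05×0.95) / 0.35² = 7.849 × 0.2875 / 0.1225 = 18.4, rounded up to 19 per arm.

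The stated size is reproduced. The SAP identifies the event as IRIS, so the 35-point difference is not a mortality assumption. The rates imply 19×0.40 + 19×0.05 = 8.55 events. The SAP lists seven covariates besides treatment.

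**Chance of imbalance.** The number K of pulmonary patients is not in the documents; I assume 8 to 23 of 38. With 19 per arm, the number x in one arm is hypergeometric, P(x) = C(K,x)·C(38−K,19−x)/C(38,19), and the arms differ by |2x−K|.

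Example, K = 15: a difference of 4 or more needs x ≤ 5 or x ≥ 10, so P = 2 × (0.0694 + 0.0189 + 0.0032 + 0.0003) = 18%.

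| K of 38 | P(differ by ≥4) | P(differ by ≥6) |
|---|---|---|
| 8 | 23% | 4% |
| 9 | 12% | 2% |
| 11 | 15% | 3% |
| 12 | 30% | 8% |
| 15 | 18% | 4% |
| 18 | 33% | 10% |
| 19 | 19% | 5% |
| 20 | 33% | 10% |
| 23 | 18% | 4% |

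Over every K from 8 to 23, the chance of 4 or more is 12-33% and of 6 or more 2-10%. The jumps between neighbouring rows arise because an odd K allows only odd differences (4 or more then means 5 or more) and an even K only even ones. Simulating the actual blocks of ten, whose fourth block stops at 8 patients, changes little: for K = 11, 15 and 19, a difference of 5 or more has probability 15.6%, 19.0% and 20.5%, against 15.1%, 18.4% and 19.4% from the formula.

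**Effect on mortality.** With mortality m₁ with and m₀ without pulmonary KS (both assumed) and no treatment effect, the expected difference between arms is d/19 × (m₁ − m₀), where d is the excess of pulmonary patients.

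- 30% v 10%: d = 4 gives 4/19 × 0.20 = 4.2 points; d = 6 gives 6.3 points.
- 50% v 10%: d = 4 gives 4/19 × 0.40 = 8.4 points; d = 6 gives 12.6 points.

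That is 0.8 to 2.4 deaths per 19 patients.

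**Effect on the test.** Simulation under no treatment effect (200,000 trials per scenario; K = 15 or 19; the same two pairs of death rates), comparing an unadjusted chi-square with a Mantel-Haenszel test stratified by pulmonary KS:

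| Allocations considered | Unadjusted | Stratified |
|---|---|---|
| All | 4.8-5.3% | 4.6-4.9% |
| One arm has ≥4 extra pulmonary patients | 6.4-10.8% | 4.4-4.8% |
| One arm has ≥6 extra | 8.1-16.7% | 4.6-4.8% |

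These are simple tests of proportions, not the planned Cox model. They show the direction and rough size of the effect.

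**The case against.** The strongest reply is that randomisation already protects the comparison. Over all allocations the unadjusted false-positive rate stays near 5%, so the trial is valid without stratification. That stands: a reader might infer that the mortality comparison is biased, and it is not. What remains is that one allocation will be realised and interpreted, and the error rate given a poor split is higher.

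Other points against:

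- **The prognostic premise is assumed.** The documents give no mortality by site, and planning a subgroup comparison does not prove a strong effect. This stands, which is why the results are ranges. The listed laboratory covariates might also absorb part of an imbalance; the documents do not say how far they track lung disease.
- **The size is easy to overstate.** A reader might count a difference of 3 or more and find about 48-52% for 11, 15 or 19 pulmonary patients. With an odd count, that only means anything worse than the best possible split. For even counts from 8 to 20 the figure is 23-33%.
- **The protocol's list is a minimum.** Its wording leaves room for a pulmonary term. However, room to add a term is not prespecification, and the later SAP list does not use it.
- **The pulmonary comparison is already planned.** It is made within pulmonary patients, so this imbalance does not confound it, and unequal numbers cost it little: a 10 v 5 split carries (10×5)/(8×7) = 89% of the information of 8 v 7. But it does not protect the overall comparison.
- **Stratified randomisation is not free.** In an open-label envelope trial, fixed blocks of four make 33% of assignments certain from earlier ones in the block, against 17% for blocks of ten. This stands, and it is why the remedy lies in the analysis.

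**Conclusion.** The concern holds as one of chance imbalance. The text establishes that eligibility is mixed, that no stratification factor is named, that no listed model has a pulmonary or disease-extent term, and that pulmonary KS is singled out for mortality. The size rests on two assumptions outside the documents: 8-23 of 38 patients with pulmonary KS, and mortality of 30-50% with it against 10% without. On those, a difference of 4 or more patients has a 12-33% chance, and a difference of 4 to 6 moves mortality by about 4-13 points. That can tip or hide a borderline mortality result.

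A reader might go further and infer that imbalance could produce an effect of the planned size. The figures do not support that: the shift is well below 35 points, and those 35 points refer to IRIS. If pulmonary KS is a weak predictor of death in this population, the shift shrinks in proportion.

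**What to change.** - In the protocol's Primary outcome section and in the SAP, prespecify baseline pulmonary KS (yes/no) as a stratum in the Cox mortality comparison and as a term in the logistic one.
- State how pulmonary KS is determined from the pre-randomisation work-up. The protocol gives no criterion, bronchoscopy is done only if indicated, and biopsy proof is required at one site, which need not be the lung.
- Use it in place of a laboratory covariate, not in addition, because few events are expected. The CD4+/CD8+ ratio in the SAP list is a natural candidate, since it overlaps with CD4+. The ratio is not in the protocol's list, so the two documents should give one agreed list.
- Report the number with pulmonary KS in each arm.
- If the outcome data have already been seen, label the result a sensitivity analysis. The SAP is written in the past tense, so this may apply.

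The cost is one laboratory covariate and a few lines of text, with no extra patients or tests. Stratified randomisation is optional and applies only while enrolment is open; it should not use small fixed blocks in this open-label envelope trial.

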**Blinding:**

No blinding was considered feasible for personnel or patients; this is an open label study.

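### Fixed blocks of ten in an open-label trial leave at least three, and on average about five, of 38 assignments deducible by anyone who knows the block size and tracks allocations

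*Protocol*

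**What the plan says.** The Randomization section of the protocol gives the whole allocation method in one sentence: "Patients will be randomized by blocks of ten; the assigned group written in closed envelopes". The Blinding section adds: "No blinding was considered feasible for personnel or patients; this is an open label study".

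The allocation ratio is not stated. It is inferred from the Sample Size section ("The number of resulting patients in each group is 19 for a total sample of 38 patients"), which the SAP repeats ("The number estimated in each group was 19, for a total sample of 38 patients").

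Neither document mentions:
- varying the block size or withholding it from recruiters;
- opaque or sequentially numbered envelopes;
- who prepared and who holds the list and envelopes;
- stratification or more than one list.

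**The concern.** In an open trial the treatment of each enrolled patient is visible. If the block size is also known and constant, the remaining places in a block can be counted down. Once one arm has filled its five places, every later place in that block belongs to the other arm. A closed envelope gives no protection, because the content is deduced without opening it.

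Recruiters have some room to act on such knowledge. Entry requires a patient "able and willing to provide written informed consent", and the long screening work-up makes the moment of entry somewhat flexible. The arms also differ visibly in when antiretroviral therapy starts, so a clinician may hold a view, in good faith, on which arm suits a particular patient. With 38 patients and mortality as the primary outcome, placing a few sicker patients in one arm could shift the result. Intention-to-treat analysis does not repair selection that occurs before randomisation.

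**Working it through.** **Inputs.** Block size 10, fixed (protocol, Randomization). No blinding (protocol, Blinding). 19 per group, 38 in total (protocol, Sample Size; SAP). Assumed: 5 + 5 places per block and one list.

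**The plan's own figure.** With rates of 40% and 5%, two-sided alpha 0.05 and power 80%, the unpooled formula gives n = (1.960 + 0.842)² × (0.40 × 0.60 + 0.05 × 0.95) / 0.35² = 18.42, rounded up to 19 per group. The stated size is reproduced. It is used here only for the total and the ratio.

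**Certain assignments in one full block.** There are C(10,5) = 252 equally likely arrangements. The last k places are forced, and no more than k, with probability 2 × C(9 − k, 4) / 252:

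| k | arrangements | probability |
|---|---|---|
| 1 | 140 | 0.556 |
| 2 | 70 | 0.278 |
| 3 | 30 | 0.119 |
| 4 | 10 | 0.040 |
| 5 | 2 | 0.008 |

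The mean is (140 + 140 + 90 + 40 + 10) / 252 = 1.67 per block. Every completed block has at least one.

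**Over 38 patients.** This is three full blocks plus eight places of a fourth. In the fourth, place 8 is forced in 42 arrangements, place 7 in 12 and place 6 in 2, so the expected number is 56 / 252 = 0.22. The total is 3 × 1.67 + 0.22 = 5.2, or 5.2 / 38 = 13.7%. The minimum is 3, one per completed block.

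**Guessing.** Always naming the arm with more places left gives 6.53 correct per full block and 4.81 in the first eight places of the fourth. That is 3 × 6.53 + 4.81 = 24.4 of 38 (64%), against 19 (50%) by chance.

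**Other block schemes.** Smaller fixed blocks are worse: 33% of places are certain with blocks of four and 25% with blocks of six. With sizes drawn at random from 8, 10 and 12, simulation with a guesser who knows the set of sizes but not their order gives about 0.6 to 0.7 certain assignments in 38 (1.5% to 1.8%). The correct-guess rate stays near 64%.

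**How far a few steered patients could matter.** This is an illustration with Fisher's exact test and 19 per arm, not the planned Cox model. The planning rates correspond to about 8 v 1 events (0.40 × 19 = 7.6; 0.05 × 19 = 0.95).

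| Direction | Events by arm | p |
|---|---|---|
| Removing a difference | 8 v 1 | 0.019 |
| | 7 v 2 (one event moved) | 0.12 |
| | 6 v 3 (two moved) | 0.45 |
| Creating a difference | 5 v 3 (one moved from 4 v 4) | 0.69 |
| | 6 v 2 (two moved) | 0.23 |
| | 7 v 1 (three moved) | 0.042 |

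**The case against.** The arithmetic is not in dispute, but its premises can be challenged. Absence of blinding does not establish that recruiters see the running tally, read the protocol text or know the block size. Equal blocks and a single list are inferences. With several lists, certainty would arise only in blocks filled far enough to exhaust one arm. This stands, and the point must be conditional.

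Ten is already a large block for 38 patients, and varied sizes do not lower the average guessing rate. That also stands. Varied blocks remove certainty and little else, so the unstated concealment arrangements matter at least as much as the block size.

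A reader might infer that steering two or three patients could readily create a mortality difference. The illustration does not support that. Removing a difference takes one moved event. Creating one takes three, and each steered patient must have the event. Suitable patients must also be available at the forced places, and the APACHE II exclusion narrows the severity range that could be exploited.

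Finally, the models adjust for baseline CD4 and HHV-8 load, and in the SAP also for HIV load, IL-6, CRP and coinfections. This covers part of the severity a recruiter could act on, but not what is unmeasured.

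**Conclusion.** The concern holds as a conditional exposure. Given one list, 5 + 5 blocks, and someone involved in enrolment who knows the block size and follows past allocations, at least 3 and on average 5.2 of 38 assignments (13.7%) are known in advance. A cheap alternative cuts this to fewer than one.

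Two stronger readings are not supported. One is that staff did know the upcoming assignments: the documents do not say who enrols, who holds the envelopes or who sees the tally. The other is that selection bias occurred: nothing in either document bears on that.

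**What to change.** **If patients are still to be enrolled.** For the remaining list, draw block sizes at random (for example 8, 10 and 12) and leave the sizes out of any text available to recruiters. Have the list and sequentially numbered opaque envelopes prepared and held by an existing staff member who does not enrol. State all of this in the protocol, together with the allocation ratio and the number of lists. These steps belong together, because varied sizes alone leave the guessing rate near 64%.

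The cost is a new list and a possibly larger final imbalance. Fixed tens stopped at 38 can differ by at most 5 − 3 = 2 patients. An unfinished block of 12 could in the worst case leave a gap of 6.

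**If enrolment is over**, as the past tense of the November 2019 SAP suggests. Report the fixed block size, the open allocation and who prepared and held the list and envelopes, and name this as a limitation. Tabulate baseline severity by position in block, as description only. About five forced assignments are too few for the absence of a pattern to reassure. The cost is one table from the allocation list and existing baseline data.

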**Blinding:**

No blinding was considered feasible for personnel or patients; this is an open label study.

**Sample Size**

Sample size was calculated for a study power of 80% and an alpha of 0.05. Event rate in the control group was estimated as 40%, while that in the treated group was considered 5%. The number of resulting patients in each group is 19 for a total sample of 38 patients. This assumes a significant impact of treatment on S-IRIS-KS occurrence and its mortality.

The antiretroviral scheme will be assigned according to the criteria of the “The Antiretroviral Management Guide of Persons with HIV” in effect in Mexico.

Candidates will have an initial thorough clinical evaluation including a work-up to diagnose coinfections and rule out other neoplasms that comprise: ophthalmologic evaluation, computed tomography (CT) scan (neck, thorax, and abdomen), bone marrow culture with bone biopsy, Hepatitis B Virus (HBV) and Hepatitis C Virus (HCV) serology, venereal disease research laboratory (VDRL) test and if indicated lumbar puncture to rule-out neurosyphilis, Histoplasma urinary antigen and serology, and GenXpert MTB/RIF test. Upper gastrointestinal tract (GIT) endoscopy with biopsy of lesions; colonoscopy will be performed only on patients with diarrhea or lower-GIT bleeding. Biopsies of enlarged lymph nodes will be obtained and processed for histopathological analysis and culture. If indicated, bronchoscopy with bronchoalveolar lavage (BAL) will be performed as well as a thoracic Gallium 67 Spect-CT Scan or PET-FDG scans.

**Criteria for Non-severe-IRIS KS and Severe-IRIS-KS**

**Non-severe-IRIS-KS:** Is defined as an increase in the number of KS lesions plus  $\geq$ one log10 of HIV-1 RNA VL decrease or  $\geq$ 50 cells/mm^3 or  $\geq$ 2-fold from baseline CD4+ cells increase after cART initiation.

**Severe-IRIS-KS:** Is defined as an abrupt clinical deterioration after cART initiation alongside the presence of at least two clinical and at least three laboratory criteria.

Clinical criteria: 1) Fever (no identified concomitant infection), 2) increase in the size or number of KS lesions, 3) exacerbation of lymphedema, 4) appearance or increase of otherwise unexplained lung opacities on the chest images with a negative Gallium-Scan negative and 4) appearance or increase of pleural effusion.

Laboratory criteria: 1) Thrombocytopenia  $<$ 100,000 platelets/ml; 2) Anemia (decrease of at least 1 g/dl from previous measure and no obvious bleeding), 3) Hyponatremia  $<$ 135 mEq/L and 4) Hypoalbuminemia  $<$ 3.5 g/dL. This is the clinical picture associated with death.

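### IRIS is counted from cART start with no time limit inside a fixed 48-week follow-up, so the arms have at most 48 and 44 weeks at risk, and no exposure term is stated

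*Protocol*

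**What the plan says.** - **Definitions** (Protocol, Criteria for Non-severe-IRIS KS and Severe-IRIS-KS). Severe IRIS "Is defined as an abrupt clinical deterioration after cART initiation", with two or more of the listed clinical signs and three or more of the laboratory signs. Non-severe IRIS needs more KS lesions together with a viral-load fall or a CD4 rise once cART has begun. Neither definition has an end date.
- **Start of cART** (Protocol, Randomization). Controls start immediately. Experimental patients "initiate cART at week 4 after randomization".
- **Follow-up** (Protocol, Primary outcome and Classification of KS evolution). Follow-up ends at 48 weeks. There is one visit schedule for both arms: baseline and weeks 1, 2, 4, 8, 12, 16, 24 and 48. Nothing extends follow-up in the experimental arm.
- **Analysis of IRIS.** For the total of severe and non-severe events, the Protocol (Secondary outcomes) says "This is going to be done by a Poisson's models analysis". The SAP applies a Poisson model to repeated severe episodes and also compares the number of patients with one or more. Neither document names person-time, an offset or a time origin.
- **Progression** (Protocol, Classification of KS evolution). Disease Progression is an increase in the number and size of lesions during follow-up. No timing rule separates it from IRIS.
- **Mortality.** The Protocol's primary outcome is death from any cause at 48 weeks. The SAP's is death attributed to S-IRIS-KS.

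**The concern.** An event that can only occur after cART is compared between arms that start cART four weeks apart and stop follow-up on the same date. Controls can therefore accrue IRIS for longer, and a comparison of raw counts starts below 1 even if valganciclovir does nothing.

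Two related gaps follow. First, an experimental patient who deteriorates, dies or leaves in weeks 0 to 4 cannot meet either definition, whereas a control patient with the same course can. The plan has no scoring rule for such patients. Second, with no upper limit, new lesions many months into effective cART fit the non-severe definition, so the Protocol's combined IRIS total can include what is really progression. This second gap is the same in both arms: it blurs what is counted rather than giving one arm less time at risk.

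At stake are the IRIS comparisons and the SAP's cause-specific mortality outcome, which depends on the same open-ended definition.

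**Working it through.** **Inputs.** From the Protocol: cART start at week 0 (control) and week 4 (experimental); end of follow-up at week 48; 19 patients per arm; planned event rates of 40% and 5%, which the SAP labels as IRIS. Assumed: weeks run from randomization, cART starts on schedule, and there is no early death or dropout unless stated.

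**1. The plan's own figure.** The Protocol states: "Sample size was calculated for a study power of 80% and an alpha of 0.05". With two-sided alpha and unpooled variance,

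n = (1.960 + 0.842)² × (0.40 × 0.60 + 0.05 × 0.95) / 0.35² = 18.4, so 19 per arm.

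This matches. No time horizon enters the formula, so the sample size does not depend on the point made here.

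**2. Time at risk.**
- Control: 48 − 0 = 48 weeks; 19 × 48 = 912 person-weeks.
- Experimental: 48 − 4 = 44 weeks; 19 × 44 = 836 person-weeks.
- Ratio: 836/912 = 44/48 = 0.917.

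**3. Count ratio with no treatment effect.**
- Events spread evenly after cART: 0.917, a built-in reduction of 8.3%.
- 90% of the 48-week cumulative hazard in the first 24 weeks after cART (assumption): the remaining 10% is spread over 24 weeks, of which the experimental arm misses 4. Ratio = 1 − 0.10 × 4/24 = 0.983.
- 90% in the first 12 weeks (assumption): 1 − 0.10 × 4/36 = 0.989.

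**4. Proportion with an event, no effect, constant hazard.** A 48-week risk of 40% becomes 1 − 0.60^(44/48) = 37.4% over 44 weeks. With 19 per arm, the chance that a two-sided Fisher test at 0.05 rejects is 2.8% when both risks are 40%, and 3.0% when they are 40% and 37.4%.

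**5. Experimental patients lost before week 4.** If such a patient is scored event-free, the observed experimental proportion falls on average by p/19, where p is the risk that patient would have had.
- p = 0.05: 0.05/19 = 0.3 percentage points.
- p = 0.40: 0.40/19 = 2.1 percentage points.
- Ceiling, if an event was certain: 1/19 = 5.3 percentage points.

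**6. Late lesions.** Take a patient with suppressed virus and a CD4 rise who develops new lesions late in follow-up. The lesion count has risen and the response criterion is met, so the non-severe definition is satisfied. If the lesions have also grown in size, so is Disease Progression. The severe definition is not met unless there is also abrupt deterioration with the required clinical and laboratory signs.

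**7. An offset alone is not enough.** If events are front-loaded, dividing by unequal person-time over-corrects: 0.983/0.917 = 1.07 and 0.989/0.917 = 1.08. A common window avoids this; an offset within it then handles early death or loss.

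**The case against.** The strongest reply is that the four-week delay is part of the randomized strategy. Comparing IRIS over 48 weeks from randomization is then a legitimate question, and starting the clock at cART conditions on something that happens after randomization. This stands. It is the reason to keep an intention-to-treat comparison from randomization alongside, and it means that the since-cART analysis cannot be read alone.

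The second reply is that the bias is small. This also stands: 0.92 is the unfavourable end of a 0.92 to 0.99 range, and the false-positive rate barely moves.

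A reader might be tempted to go further in four ways that the documents do not support:
- **That patients lost before cART are counted as event-free.** Neither document says so. Intention to treat makes it plausible, but the scoring rule is simply absent.
- **That each such loss costs 5 percentage points.** That is the ceiling; the expected amount is 0.3 to 2.1 points.
- **That late progression counts as IRIS generally.** This applies directly only to non-severe IRIS, and so to the Protocol's combined total. The SAP's counts of severe episodes are less exposed.
- **That the missing window is itself unequal between arms.** Its wording is the same for both; only the time at risk differs.

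**Conclusion.** The point holds as a modest but real flaw in how IRIS events are counted. Followed as written, the plan gives at most 48 weeks at risk in the control arm and 44 in the experimental arm, with no exposure term. With no drug effect the expected count ratio is 0.92 if events are evenly spread, and about 0.98 to 0.99 if 90% of the hazard falls in the first 12 to 24 weeks after cART. The direction favours the experimental arm. A reader might infer that this alone could produce the hoped-for result; it could not, being far smaller than 40% versus 5%.

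Two further gaps do not depend on that ratio: the unstated scoring of experimental patients who die or leave before week 4, and, in both arms, the overlap of non-severe IRIS with Disease Progression.

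The Protocol's all-cause mortality outcome is unaffected. The SAP's death attributed to S-IRIS-KS inherits the open-ended definition, and experimental deaths before cART cannot be attributed to S-IRIS-KS at all.

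The 48 and 44 weeks assume on-schedule cART and a clock that runs from randomization. The timing of the hazard is assumed, since the documents give none.

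**What to change.** In the SAP:
1. Count IRIS events over a common window from each patient's own cART start, of at most 44 weeks, the longest period both arms share. Use log person-time since cART within that window as the Poisson offset.
2. Add a shorter early window, fixed in advance, as a sensitivity analysis. This also shows how far late lesions drive the non-severe count.
3. Report by arm the number who never started cART and the deaths before cART, and state how these patients are scored.
4. Keep an intention-to-treat comparison of all randomized patients over 48 weeks from randomization alongside.

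**Cost.** The change is wording and one model term. It needs dates of cART start and of each event, and it leaves the sample size unchanged. Control events between weeks 44 and 48 drop out of the windowed count. The since-cART analysis excludes patients who never start cART, for whom the offset is undefined. It therefore conditions on a post-randomization event and must be read with item 4.

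**What it does not cure.** In the first four weeks after cART, controls have three scheduled visits (weeks 1, 2, 4) and experimental patients one (study week 8). The Protocol's unscheduled re-evaluation for KS exacerbation offsets this only in part, so it should be stated as a limitation.
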